12. ASSESSMENT OF EFFICACY

12.1 Primary Endpoint: Survival

All patients will be monitored for survival by recording their visits during routine follow up for response to treatment. The visits are scheduled to occur every four months from the first imaging study confirming complete ablation until month 25 or radiological progression, whichever comes first. If patients have not demonstrated radiological progression at month 25 then the imaging visit schedule is reduced to every six months until progression. Survival is confirmed at every imaging visit.

Once radiological progression is confirmed then follow up for overall survival is required. Sites are required to confirm contact with the subject during either a clinic visit or a telephone contact every three months. It is expected that subject follow up will be about five years.

12.2 Secondary Endpoint: Progression Free Survival

The protocol incorporates modified RECIST (mRECIST) developed for HCC clinical research as a basis to evaluate tumor response. The mRECIST enables assessment of overall response by taking into account target lesion response, and presence or absence of new lesions. A separate imaging manual and imaging training program has been developed for this study in order to ensure uniformity in imaging technique and imaging review in accordance with mRECIST.

12.3 Baseline Assessment

The baseline assessment must include a comprehensive evaluation of the chest, abdomen and pelvis. The HCC tumor identified on the eligibility scan should be defined as target lesion and its longest diameter should be measured on the contrast-enhanced CT or contrast-enhanced MRI scan. This measurement should reflect the overall longest tumor diameter, regardless of the presence of internal areas of spontaneous necrosis. In the study protocol, intermediate size is defined as a tumor lesion larger than 3.0 cm but not exceeding 7.0 cm in longest diameter. Since the study will recruit patients with solitary tumors and no evidence of vascular invasion or extrahepatic spread, the eligible size HCC lesion detected on the eligibility scan is expected to be the only target lesion. No additional target or non-target lesions should be detectable on the eligibility scan to allow enrollment in the study.

12.4 Target Lesion Response and Local Recurrence

The image acquisition protocols used for any post-baseline assessments should be consistent with the protocol used for the baseline eligibility scan. Baseline images for treatment eligibility will be confirmed centrally before RFA treatment. Investigator determined radiological confirmation of complete ablation will occur at one month post RFA. If initial RFA is incomplete then a second, and final, attempt may be made for a complete ablation for subject to stay on protocol. Once a complete ablation is confirmed then patients are monitored radiologically until progression. The imaging interval will be every four months until month 25 then every six months thereafter. No imaging studies are required once progression is confirmed.

The disappearance of any intratumoral enhancement in the target tumor lesion after treatment with study treatment will be classified as complete response (CR), while the persistence of any areas of intratumoral enhancement consistent with residual viable tumor will be considered as incomplete response (IR). Failure to achieve a CR after two RFA \pm ThermoDox treatment sessions will be classified as treatment failure. Tumor recurrence detected within or around the target lesion after having achieved initial CR will be classified as local recurrence. Tumor recurrences will be defined as local if they are located 1 cm or less from the ablation margin

12.4.1 Response Criteria for Assessing Index Lesion

PFS will be measured from the date of randomization to the first date on which one of the following occurs:

- Death of any cause
- Treatment failure (inability to achieve CR after two RFA \pm ThermoDox treatment sessions)
- Progression due to local tumor recurrence after initial CR
- Progression due to distant intrahepatic tumor recurrence
- Progression due to extrahepatic tumor recurrence

Disease progression will be assessed locally at each study site. CT or MRI scans (chest, abdomen, and pelvis) will be done at baseline and post-treatment at months 1, 5, 9, 13, 17, 21, 25, then every 6 months (+/- 2 weeks) until radiological progression is seen. The definitions below will be used to assess disease progression. All imaging scans must be submitted centrally. Progression must be documented prior to any non-study HCC treatment.

Table 3: Radiological Progression Definitions

Complete Response (CR):	Complete disappearance of viable tumor on follow-up scan (Day 28) when compared to the pretreatment images. The ablation zone is defined radiographically as a homogeneous, avascular, non-enhancing, sharply marginated ablation site following RFA evaluated on both arterial and portal venous phases and complete disappearance of the lesion. Ablation zones that are larger than the tumor (including a rim of surrounding liver parenchyma) are intentionally created to reduce the risk of local recurrence and are a much better predictor of actual complete ablation than is an ablation zone that is only equal in size to the native tumor.
Incomplete Response (IR):	Incomplete Response (IR): Any image-detected residual viable tumor at or within 1 cm of the ablation zone on Day 28 scan following initial ablation therapy that is smaller in size compared to pre-treatment scans, irrespective of the size of the zone of ablation. Incomplete responses will be allowed to be re-treated once.
Local Recurrence (LR):	Local recurrence (LR): Recurrence of viable tumor at or contiguous (within 1 cm) to the site of a prior ablation in the liver based on meeting one of any of the specific imaging criteria and features listed below when comparing the recent imaging (latest) to the reference imaging (Day 28 post-RFA, assuming complete treatment on Day 28 scan): 
• New soft tissue attenuation nodules that abnormally enhance and washout following intravenous contrast administration.• On subsequent scans at time points longer than 4-6 weeks after RFA: Presence of a measurable increase (at least 10 mm) in size of the abnormally enhancing nodular soft tissue component within or adjacent to the treated tissue, as compared with baseline scan at approximately Day 28 post-RFA.• A new HCC lesion or nodule signifying local recurrence is defined as a hypervascular lesion or nodule with abnormal enhancement and washout as defined above, and measuring greater than 10 mm in any axial dimension.• A lesion that does not show the prior typical features of HCC, but demonstrates serial enlargement of at least 10mm.
Distant Hepatic Recurrence (DHR):	Development of a new lesion (meeting the criteria described above for a new lesion) in the liver at a site greater than 1 cm from a prior ablation site, compared with nadir.

Extrahepatic Recurrence (EHR):	Appearance of a new lesion outside of the liver. Note: extrahepatic HCC lesions may not demonstrate the same enhancement criteria as indicated for intrahepatic lesions; however, they should be unequivocally malignant and new since nadir. There are no size criteria.
Unable to Evaluate (UE):	A lesion present at baseline which was not measured or which was unable to be evaluated leading to an inability to determine the status of that particular tumor for the time point in question.
Not Done (ND):	Scans were not performed at this time point to evaluate the lesions.
Equivocal (EQ)	A new liver lesion that is smaller than 1 cm in longest diameter OR fails to show a typical enhancement profile should be considered as equivocal and not conclusive for disease progression. Such lesions can be diagnosed as HCC by evidence of either a change in enhancement pattern OR at least 1-cm interval growth in subsequent scans.

Table 4: Overall responses for possible combinations of tumor responses in the target lesion with or without the appearance of new intrahepatic or extrahepatic lesions.

Target Lesion	Distant Intrahepatic Recurrence	Extrahepatic Disease	Overall Response
CR	No	No	CR
IR*	No	No	Treatment Failure
IR*	Yes	No	Progression
IR*	No	Yes	Progression
Local Recurrence	Yes or No	Yes or No	Progression
Any	Yes	Yes or No	Progression
Any	Yes or No	Yes	Progression

*After 2 RFA +/- ThermoDox treatment sessions within 21 days after Day 28 radiological examination.

13. ASSESSMENT OF SAFETY

Safety data will be tabulated for all subjects who were treated under the study protocol in either treatment group and will include vital signs, laboratory parameters, ECG, echocardiograms/MUGA, and adverse events. The Principal Investigator is responsible for recognizing and reporting adverse events during the conduct of the trial.

A Data Monitoring Committee (DMC) will evaluate safety data on an ongoing basis at regular intervals during subject accrual and follow-up. The DMC is responsible for unblinded monitoring of subjects with elevated (> 2.0 mg/dL and ≤ 3.0 mg/dL) serum bilirubin levels and will advise if any dose or protocol modification is needed to mitigate risk to such patients. The Sponsor is responsible to report relevant SAEs to applicable local, national, and/or international regulatory body.

14. ADVERSE EVENTS

An adverse event is defined as any unfavorable and unintended sign, including an abnormal laboratory finding, symptom, or disease temporally associated with the use of an investigational product, whether or not related to the investigational product. This includes any occurrence that was new in onset or aggravated in severity or frequency from the baseline condition. Adverse events (AEs) assessments will begin at time of signing of informed consent and will continue through Day 28 following study drug administration. AEs which are assessed as possibly, probably, or definitely related to study drug must be followed until resolution or until a stable clinical endpoint is reached.

Other safety data including physical examinations, vital signs, ECGs, echocardiograms/MUGA scans, hematology, clinical chemistry, and urinalysis will be assessed through Day 28 following study treatment. Subjects with an elevated serum bilirubin level (> 2.0 and ≤ 3.0 mg/dL) at baseline will have additional safety assessments at Day 7 post-ablation and at any other time the physician deems it necessary.

To provide surveillance for any late hematologic, cardiac, or liver toxicity, the following additional safety assessments will be done:

- Physical examination, assessment of vital signs, ECGs, CBC with differential, serum chemistry, PT/INR and urinalysis at Month 5, Month 9, and Month 13 (+/- 2 weeks) or at disease progression, whichever occurs first.
- LVEF monitoring at Month 13 or at disease progression, whichever occurs first
- Serum chemistry and PT/INR assessments at Month 17, Month 21, and Month 25 (+/- 2 weeks) or at disease progression, whichever occurs first.

The condition which is detected by the diagnostic procedure conducted to test the efficacy of the investigational agent is not considered an AE.

Symptoms or clinically significant laboratory or instrumental (e.g., electrocardiographic) abnormalities of a pre-existing disease, such as cancer or other disease, should not be considered an AE. However, occurrence of new symptoms or laboratory or instrumental abnormalities, as well as worsening of pre-existing ones, are considered AEs.

Abnormal results of diagnostic procedures, including laboratory test abnormalities, are considered adverse events if they result in:

- Treatment or any other therapeutic intervention.
- Further diagnostic evaluation (excluding a repetition of the same procedure to confirm the abnormality).
- Associated clinical signs or symptoms that would have a significant clinical impact, as determined by the Investigator.

Any untoward medical event that occurs from the time of signed informed consent to the time immediately prior to the first study drug administration will be reported as a “predose event” in the Medical History CRF.

All adverse events that occur following study drug treatment will be documented on the AE CRF with indications of onset, duration, severity (NCI Common Terminology Criteria for Adverse Events), presumed relationship to study medication/RFA (not related, unlikely, possibly, probably, definitely), remedial actions taken, and outcome.

An adverse event will be considered associated with the use of the study drug/RFA if the attribution was possibly, probably, or definitely.

All subjects will be encouraged to report adverse events spontaneously or in response to general, open-ended questioning. All adverse events which are assessed as possibly, probably, or definitely related to study drug are to be followed up until resolution or the patient is clinically stable.

Adverse events will be graded according to NCI Common Terminology Criteria for Adverse Events (CTCAE) Version 4.03 (See Appendix IX).

14.1 Laboratory Test Results

Clinically significant laboratory or instrumental (e.g., electrocardiographic) abnormalities of a pre-existing disease, such as cancer or other disease, should not be considered an AE. Any laboratory test result considered by the Investigator to be unusual, associated with clinical signs and/or symptoms, and clinically significant should be reported as an adverse event (clinically significant adverse events include those which require an intervention). Grade 3 laboratory abnormalities meeting the above description should be recorded as AEs. All grade 4 abnormal laboratory results must be recorded as AEs.

Significant abnormal values occurring during the trial will be followed until repeat test results return to normal, stabilize, or are no longer clinically significant. Any positive

pregnancy test result must be repeated, study treatment withdrawn, and any pregnancy must be followed to term.

14.2 Overdose

Any instance of overdose (suspected or confirmed) must be communicated to the medical monitor within 24 hours of knowledge and be fully documented as a serious adverse event. An overdose should be evaluated by the Principal Investigator and potentially reported as an unanticipated problem to the site's IRB according to local requirements.

An overdose in which signs, symptoms, or abnormalities meet the definition of an adverse event or serious adverse event must be fully documented and reported consistent with AE and SAE reporting guidelines. Details of any signs or symptoms and their management must be recorded in the CRF.

14.3 Non-Serious Clinical Adverse Events

A **non-serious adverse event** is any AE that does not meet the criteria listed in section 14.4 for a serious AE or the outcome (i.e., subject treatment, life-threatening condition, hospitalization, recovery) cannot be determined with the information provided.

For detailed description of relationship of AE to study treatment refer to Appendix V.

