14.4 Serious Adverse Events (SAE)

Serious adverse events are defined as any untoward medical occurrences that at any dosage results in one or more of the following:

- Death.
- Is immediately life-threatening, (i.e., presented an immediate risk of death at the time of the adverse event, not an adverse event that hypothetically might have caused death if it were more severe).
- Requires or prolongs inpatient hospitalization.
- Causes persistent or significant disability/incapacity.
- Is a congenital anomaly/birth defect.
- Significant medical event that requires intervention to prevent one of the above outcomes listed in the above definition

Any SAE, which occurs after a subject has signed consent and until Day 28 following last study drug administration, whether or not related to study treatment, must be reported to Pharmacovigilance immediately (within 24 hours of knowledge of the event) via telephone, facsimile or email. If initially reported via telephone or email, this must be followed up by a facsimile of the written SAE report (within 24 hours of the initial telephone report).

Country specific reporting requirements apply. For example, all China local SAEs during the study must be reported within 24 hours to the CFDA.

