14.4.3 Reporting of SAEs

Any serious event, including death from any cause that occurs up to one month following last study treatment administration, whether or not related to the investigational drug or RFA, must be reported to Pharmacovigilance immediately (within 24 hours) via telephone, fax, or e-mail.

If initially reported via telephone or e-mail, this must be followed-up by a written faxed report to be submitted within 24 hours of the initial report.

Pharmacovigilance (SAE) contact phone numbers:

InVentiv Pharmacovigilance

Region	North America	Mainland China	Europe & Rest of World
Fax (SAE reporting)	[REDACTED]	[REDACTED]	[REDACTED]
Email	(NA) [REDACTED] (ROW/Asia Pac)		

Initial Reports

Within 24 hours of the site's knowledge of a serious adverse event:

- Complete a Serious Adverse Event Report Form (SAER), sign it, and fax it to the Pharmacovigilance using the designated fax transmittal form.
- Place the initial version of SAER in the subject's file.

Follow-Up Reports

New information received spontaneously or by request of the Medical Monitor or Safety Surveillance:

Within 48 hours of the receipt of new information:

- Complete a new SAER with the new information. Sign and fax the form to Pharmacovigilance.
- Fax copies of supporting documents (e.g., hospital discharge summaries, lab test results with normal ranges, autopsy or biopsy reports) to Pharmacovigilance.
- Place the follow-up version of the SAE and all supporting documentation in the subject's file.

Final Report

Within 48 hours of the receipt of final information:

- Determine that there is no further information available and this update may be considered final.
- Complete a new SAER form with the new and final information. Sign and fax the form to Pharmacovigilance. As above, send copies of any additional supporting information.
- Place this version of the final SAER into the subject's file.

It is imperative that Pharmacovigilance be informed within 24 hours of a serious adverse experience (including overdose with clinical effect, which is considered an SAE) so that reporting to the FDA and other regulatory agencies can be met within the required time frame (7 or 15 calendar days).

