Because of the need to report to health authorities all serious adverse experiences in a timely manner, it is vitally important that an Investigator report immediately any adverse experiences, which would be considered serious, even if the Investigator does not consider the adverse experience to be clinically significant or drug/RFA-related.

Should the Investigator become aware of an SAE (regardless of relationship to study drug) that occurs while the subject is on the study, the SAE must be reported in accordance with the procedures specified in this protocol.

If the subject is withdrawn less than 28 days after study drug treatment, any SAEs which occur within 28 days after study drug treatment must be reported in accordance with the procedures specified in this protocol.

All serious adverse events that are assessed as possibly, probably, or definitely related to study drug are to be recorded at any point during the trial and followed until either: the adverse event resolves, the adverse event stabilizes, the adverse event returns to baseline

values (if a baseline value is available), or it is shown that the adverse event is not attributable to the study drug or study conduct.

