6.1.2.2 Missing Data

All analysis will be based on available data to summarize safety and efficacy results. However, a conservative approach to partial dates and missing adverse event's relationships will be as follows:

- For the OS analyses, if a subject's death month and year are provided but the day is missing, the day will be set to the first day of the month, unless other qualifying study data support survival until a later date in the same month. The same concept will be applied if only the year is known. For a completely missing date of death, the fatality will be imputed to have been occurred on the last available contact of the subject where we still know he/she was alive.
- Adverse events with partial dates with the same month and year as the Procedure Day 0 will be considered as treatment-emergent adverse events.
- If an adverse event's relationship is missing it will be assumed to be related.

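### Protocol 14.3 makes an adverse event non-serious when life-threatening status or hospitalisation cannot be determined, which conflicts with 14.4 and takes it outside the mandatory 24-hour report

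*Protocol*

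**What the plan says.** Protocol 14.3 says that a non-serious adverse event "is any AE that does not meet the criteria listed in section 14.4 for a serious AE or the outcome" cannot be determined. The second alternative reads in full: "the outcome (i.e., subject treatment, life-threatening condition, hospitalization, recovery) cannot be determined with the information provided".

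Protocol 14.4 lists the criteria that make an event serious. Two of them are "Requires or prolongs inpatient hospitalization" and "Is immediately life-threatening, (i.e., presented an immediate risk of death at the time of the adverse event". The last covers significant medical events that need intervention to prevent one of the other outcomes. Any SAE between consent and Day 28 after the last study drug administration "must be reported to Pharmacovigilance immediately (within 24 hours of knowledge of the event) via telephone, facsimile or email".

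Protocol 14.4.3 repeats the duty: "It is imperative that Pharmacovigilance be informed within 24 hours of a serious adverse experience". It adds that "it is vitally important that an Investigator report immediately any adverse experiences, which would be considered serious", even where the investigator doubts clinical significance or relatedness. It also sets out follow-up reports, due within 48 hours of new information. Protocol 14.5 leaves expedited reporting in other situations to medical and scientific judgement.

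Two neighbouring rules take the cautious side when facts are missing. Under Protocol 14.2 a suspected overdose must be communicated within 24 hours and documented as an SAE. SAP 6.1.2.2 says: "If an adverse event's relationship is missing it will be assumed to be related".

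**The concern.** A definition of non-serious should be the complement of the definition of serious. Here it also takes in events whose seriousness is still open, so missing information settles the classification in the less cautious direction.

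Missing information is foreseeable in this trial. After discharge, scheduled visits fall on Days 14 and 28, with a Day 7 visit only for subjects with elevated baseline bilirubin (Protocol 5.1). An acute event between visits may be treated elsewhere, before the site has records. The adverse event outcome codes in Protocol Appendix V include one for an outcome that could not be determined.

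Two things are at stake: the timeliness of SAE reports to pharmacovigilance, and the completeness of the SAE summaries planned in Protocol 15.3.2.4 and SAP 6.4.1.

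**Working it through.** No arithmetic applies, because the point concerns a definition and the duty that hangs on it. The check sets the sections side by side.

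**1. What the second alternative adds.** The first alternative in 14.3 already covers every event shown to fall outside 14.4. The second is joined by *or*, so it can add only events not shown to fall outside 14.4. Those are the ones whose seriousness is unresolved.

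**2. Items in the 14.3 parenthesis against 14.4.**

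| Item that cannot be determined (14.3) | Place in 14.4 |
|---|---|
| Life-threatening condition | A seriousness criterion |
| Hospitalisation | A seriousness criterion |
| Subject treatment | Not a criterion, but bears on the intervention criterion |
| Recovery | Not a criterion |

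Two of the four items are facts that decide seriousness. Not knowing them should leave the question open, whereas 14.3 closes it.

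**3. From classification to reporting.** Section 14.3 contains no reporting instruction, so its effect runs through the label. The duty in 14.4 attaches to any SAE. The duty in 14.4.3 attaches to any serious event and to experiences that would be considered serious. An event that 14.3 labels non-serious does not trigger either.

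**4. Whether another provision reverses the default.**
- *14.4, clock from knowledge of the event.* This fixes when the 24 hours start, but the subject of the sentence is still an SAE.
- *14.4.3, immediate reporting despite doubt.* The doubts it overrides concern clinical significance and relatedness. It does not address doubt about seriousness.
- *14.4.3, follow-up reports.* These allow an incomplete first report to be completed, once the event is in the SAE process.
- *14.5, judgement on expedited reporting.* This is discretionary, and its example is important medical events, not missing information.

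None of these says that an event of unknown seriousness is handled as serious until clarified.

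**5. Comparison with the documents' other defaults.** Suspicion alone triggers 24-hour communication for an overdose (14.2). A missing relationship is assumed related (SAP 6.1.2.2). Undetermined seriousness is the one that falls the other way.

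**6. Consequence for the analyses.** If the facts arrive later and meet 14.4, the event becomes an SAE and is reported then, so the effect is delay. If they never arrive, the event stays non-serious and is missing from the separate SAE summaries. It would still appear in the all-event tables, and in the Grade 3 and 4 tables if graded so. OS depends on death, and PFS on radiological progression, treatment failure or death. Neither uses the seriousness label.

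**The case against.** The best defence is that 14.3 is a garbled sentence and not an intended rule. Taken literally, it would make a hospitalised patient non-serious merely because recovery was unknown, which flatly contradicts 14.4. A sensible investigator would follow 14.4 and 14.4.3, where the reporting instructions sit. Those sections start the clock at knowledge of the event and expect incomplete first reports, with documents such as discharge summaries to follow. Section 14.5 also invites judgement. This stands in part: it narrows the practical gap and makes delay the usual harm. It does not remove the conflict, because nothing tells a site which section prevails when seriousness is unknown.

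A reader might infer more than the documents support in four ways:
- *A count of affected events.* The roughly 2% major complication rate in Protocol 3.2, applied to 550 subjects, gives 0.02 × 550 = 11. The documents give no share of these that would first present with undetermined seriousness. The complications named there are established diagnoses whose seriousness would usually be evident.
- *That every such event is a missed or late expedited report to regulators.* Protocol 14.4.3 mentions 7 and 15 calendar days but does not say which SAEs start those clocks.
- *That any collapse treated at an outside hospital would escape reporting.* Such an event could readily be judged to meet the intervention criterion in 14.4.
- *That an SAP rule imputing missing seriousness would repair the tables.* An event recorded as non-serious under 14.3 has no missing seriousness, so the rule would not find it. An SAP rule also cannot change what sites report.

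**Conclusion.** The point holds as a conflict between Protocol 14.3 and 14.4, and it should be corrected. As written, events whose life-threatening status or hospitalisation is undetermined are non-serious and fall outside the mandatory 24-hour SAE report. The follow-up and discretionary provisions soften this but do not override it.

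The usual consequence is a late SAE report. Where information never arrives, there may be no SAE report and the SAE summaries are undercounted. The number of events cannot be estimated from the documents, and the OS and PFS analyses are unaffected.

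The conclusion rests on reading 14.3 as it stands. It also assumes that no site-facing document sets a different default. The CRF completion guideline mentioned in Protocol 16.3 is not among the documents, so how seriousness is captured there is unknown.

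**What to change.** - **Protocol 14.3:** delete the second alternative, so that a non-serious event is simply one that does not meet 14.4.
- **Protocol 14.3 or 14.4:** state that an adverse event whose seriousness cannot yet be determined is reported as serious within 24 hours of knowledge, and downgraded if later information shows otherwise. This matches the treatment of suspected overdose and of missing relationship.
- **Existing data:** query events already recorded as non-serious with an undetermined outcome, so that the SAE tables are right. The Appendix V code for unknown outcome is a starting point for finding them.

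The cost is more than the sentence itself. Under Protocol 18.1 an amendment goes through the same review and approval as the original protocol, and Protocol 6.1 plans approximately 100 centres. There is also the query work, and a few SAE reports will later be downgraded. The change affects classification and reporting only.
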